## Primary outcome definition

Number of days alive outside of the hospital during the 90 days following randomisation. The outcome is countable with a minimum value of 0 and a maximum of 90. In case of death before the end of follow-up, the participant will be assigned the number of days they were outside of the hospital until death occurred. If the participant dies during the index admission, they will be assigned 0 days alive and outside of the hospital (Auriemma et al., 2021; Granholm et al., 2023). We anticipate 95% of participants to be discharged from the hospital [5–7] and based on limited previous observation data in patients with heart failure-related pleural effusion necessitating thoracentesis, we anticipated 78-91% of participants to survive 30 days after hospitalisation [1,2].

## Missing data for the primary outcome

Complete follow-up of all enrolled participants will be attempted. Primary endpoint data regarding death and admission days will be collected from the participant's electronic medical record regardless of whether questionnaire follow-up was completed. Therefore, we anticipate complete data for the primary outcome since the only way that data will not be available is due to immigration within the 90-day follow-up and investigators not being able to get in contact with the participant. The extent of missing primary outcome data will be reported. The main analysis will be a complete case analysis on data as observed. In case of missingness for the primary endpoint, sensitivity analysis will be conducted for the best-worst and the worst-best case scenario. For this purpose, we define a “harmful outcome” (worst) as no further days alive since the participant was lost to follow-up. A “beneficial outcome” (best) will be that the participant was alive and out of the hospital for the rest of the period from they were lost to follow-up till the end of the follow-up.

## Missing data for the secondary outcome

The extent of missing outcome data will be reported and discussed. Missing data from questionnaires on quality of life and patient satisfaction are anticipated and, in some cases due to the participants being deceased. The number and percentages of participants that completed questionnaire follow-up at 14 days and 90 days will be reported. For participants who did not complete the questionnaire during follow-up, an explanation will be provided if available. If an entire questionnaire is missing, we assume that this could be due to deteriorating health or death and the data is therefore missing not at random (MNAR) [15]. The main analysis will be as observed, and sensitivity analysis will be conducted for the best-worst and the worst-best case scenario. Patients who have died will be assigned the worst score (0), and patients who are alive and have not responded despite efforts to collect data (electronic reminders and telephone contact) are assumed to be of very poor to poor health and assigned the worst score (0). Missing data from

questionnaires on satisfaction with hospital stay (Likert scale 1-5, 5 representing highest satisfaction) follows the same assumption as KCCQ with data MNAR. However, it is not assumed that patients with poor health status or who die during follow-up necessary were dissatisfied with their treatment. Therefore, simple mean imputation will be used.

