### Sample Size

For estimation of sample size, we assumed a t-test of superiority and found a total of 126 participants required to detect a difference of three days in the primary endpoint with an  $\alpha$  of 0.05 and a power of 90%. This assumes, that participants assigned to a strategy with referral to up-front thoracentesis in addition to pharmacological therapy will have 85 days alive and not hospitalised during the 90 days after randomisation, while participants assigned to pharmacological therapy alone will have 82 days, with a shared standard deviation of 5 days, and in-hospital mortality of 5% in both groups [5–7]. For analysis of the primary endpoint, we will assess the Mann-Whitney parameter for days alive without hospitalisation during the 90 days following randomisation, using the Wilcoxon-Mann-Whitney-test [30]. The loss of power with the Wilcoxon rank sum test compared to the t-test is often limited if distributions are normal, and when normality is violated, the Wilcoxon rank sum test can be three or four times more powerful than the independent samples t-test [31,32]. The power of 90% will allow for a possible small loss of power from using the Wilcoxon-Mann-Whitney test.

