### Statistical principles

All outcomes are tested for superiority. A two-sided p-value  $<0.05$  is considered statistically significant, and a 95% confidence interval (CI) is reported for all effect estimates. No multiplicity adjustment will be applied.

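### Satisfaction scores assumed missing not at random are filled with an unspecified mean, and the KCCQ best-worst and worst-best scenarios have no 'best' value

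*SAP*

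**What the plan says.** The SAP section 'Missing data for the secondary outcome' covers both questionnaires. It expects missing questionnaires, partly because of death, and treats a wholly missing questionnaire as missing not at random (MNAR). It then says: "The main analysis will be as observed, and sensitivity analysis will be conducted for the best-worst and the worst-best case scenario".

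For KCCQ, participants who have died get 0. Living participants who do not respond despite reminders also get 0, on the assumption that they are in poor health. Neither rule differs by arm, and no favourable value is given.

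For satisfaction, missingness "follows the same assumption as KCCQ with data MNAR". The SAP adds that poor health or death need not mean dissatisfaction, and concludes: "Therefore, simple mean imputation will be used".

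Two other sections matter. 'Missing data for the primary outcome' defines both extremes for the primary outcome. The worst is no further days alive, and the best is that the participant was "alive and out of the hospital for the rest of the period from they were lost to follow-up" to the end of follow-up. 'Statistical principles' tests all outcomes for superiority and says that a 95% "confidence interval (CI) is reported for all effect estimates".

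**The concern.** The satisfaction rule conflicts with its own premise. If non-responders differ systematically from responders, giving them the responders' average assumes the opposite. The filled-in constants also add apparent sample size and reduce apparent variance, so any interval from the completed data is too narrow. The unstated choice of mean matters because the arm mean and the overall mean fail in different ways. The trial is open-label, so leaving the choice of mean and its place in the analysis until the data are seen is avoidable discretion.

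The KCCQ rule does not deliver the scenarios it names. A best-worst or worst-best analysis needs a favourable value in one arm and an unfavourable value in the other. With 0 for everyone, the result is driven by the arm difference in non-response and cannot show how far the effect could move in each direction. Under an MNAR assumption, that range is what the reader needs.

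**Working it through.** The SAP gives no figure for questionnaire non-response, so there is no stated result to reproduce. Missing rates, score distributions and the KCCQ mean below are assumptions.

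**Inputs from the SAP**
- 126 participants at 1:1 allocation, so 126/2 = 63 per arm ('Sample Size', 'Study design').
- Two-sided 5% level ('Statistical principles').
- t-test or Wilcoxon-Mann-Whitney test for continuous scores ('Analyses of Secondary Outcomes').
- Scales 1-5 and 0-100 (outcome table).

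**Satisfaction.** Let p be the observed fraction, with data missing completely at random, equally in both arms, and SD 1.

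- As-observed SE = sqrt(2/(63p)). After filling in a mean, the variance shrinks to about p over 63 apparent observations, so the reported SE is about sqrt(2p/63). The ratio is p, so the interval is 10/20/30% narrower at p = 0.9/0.8/0.7.
- *Arm means.* The estimate and its true SE do not change; only the reported SE shrinks. Type I error = 2 × (1 − Φ(1.96p)).
- *Overall mean.* The estimate becomes p × d, and its true SE also shrinks to sqrt(2p/63), so the level holds when d = 0. For d = 0.5 the bias is (1 − p) × 0.5 = 0.05/0.10/0.15, against an SE of 0.169/0.159/0.149.

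| Missing | CI width v as observed | Arm mean: t-test type I error | Overall mean: estimate of a true 0.5 | Overall mean: CI coverage at 0.5 |
|---|---|---|---|---|
| 10% | 0.90 | 7.8% | 0.45 | 94.0% |
| 20% | 0.80 | 11.7% | 0.40 | 90.4% |
| 30% | 0.70 | 17.0% | 0.35 | 82.8% |

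Simulation with 5,000 trials per setting and five assumed Likert distributions (means 3.0 to 4.35) agrees. Results for 10/20/30% missing, with no true difference:
- Arm means, t-test: type I error 7.1-8.0/11.3-12.6/17.2-17.7%.
- Arm means, Wilcoxon-Mann-Whitney: 6.0-21.5/11.6-44.2/28.6-59.1%. Each arm's imputed block is tied at its own value, which a rank test reads as a difference. If arm means are rounded to a Likert category, the ranges are 5-18/5-41/5-51%.
- Overall mean: 4.2-5.6% with either test.
- As observed: 4.2-5.8%.

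A separate simulation with one left-skewed item gave relative widths of 0.90/0.79/0.69, arm-mean coverage of 92.5/88.9/84.2%, and arm-mean Wilcoxon-Mann-Whitney error of 15/31/43%.

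**KCCQ.** Assume a responders' mean of 60 in both arms and equal deaths. Let a be the living non-response in each arm. Differences are intervention minus control.

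- All-zero difference = 60 × (a_control − a_intervention).
- Best-worst adds 100 × a_intervention; worst-best subtracts 100 × a_control.

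| Living non-response (intervention v control) | All zero, as written | Best-worst | Worst-best |
|---|---|---|---|
| 10% v 10% | 0 | 0 + 10 = +10 | 0 − 10 = −10 |
| 10% v 20% | 60 × 0.10 = +6 | 6 + 10 = +16 | 6 − 20 = −14 |

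**How much missingness is certain.** 'Sample Size' assumes "in-hospital mortality of 5% in both groups", or 0.05 × 63 ≈ 3 participants per arm, who cannot reach a questionnaire sent 14 days after discharge. 'Primary outcome definition' states: "we anticipated 78-91% of participants to survive 30 days after hospitalisation". That leaves 9-22% dead by then and without a day-90 KCCQ.

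**The case against.** The strongest reply is that the main analysis is probably untouched. The sentence making the main analysis as observed stands in a paragraph about both questionnaires. Mean imputation then reads most naturally as the satisfaction counterpart of the KCCQ zeros, inside the sensitivity analysis. That is a fair reading, but the satisfaction text ends with an unqualified rule and nothing else in the SAP settles it. Even as a sensitivity analysis, it would report false precision and would not probe the MNAR assumption.

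The inflated error rates need arm means, which the SAP never mentions. This stands: with the overall mean the level is kept and the bias is towards no difference. The interval is still too narrow around a diluted estimate.

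The missing rates are assumed, and the calculations use missingness completely at random, so they measure the cost of the method and not the MNAR bias. This also stands. At the 5% that in-hospital death alone implies, the interval is about 5% narrower and the arm-mean t-test error is 2 × (1 − Φ(1.96 × 0.95)) ≈ 6.3%, which is small.

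For KCCQ, an analyst could infer 100 as the best value from the scale in the outcome table. But the explicit 0 for every living non-responder would still contradict the scenario names. Deaths do not bear on the missing best value, since they stay at 0 in any case.

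**Conclusion.** The concern holds. As written, the satisfaction rule contradicts its MNAR premise, leaves the mean and its place in the analysis open, and understates uncertainty by about the missing fraction wherever the imputed data are used. Type I error rises only with arm means; with the overall mean, the harm is dilution of a true difference and loss of coverage. The KCCQ text names two opposing scenarios but specifies one worst-worst analysis, which at 10% v 20% non-response shows +6 where the bounds run from −14 to +16.

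The sizes rest on assumed missing rates of 10-30%, missingness completely at random for satisfaction, and a KCCQ responders' mean of 60 with equal deaths. The direction of each problem does not depend on the exact rates. Only secondary questionnaire outcomes are involved; the primary outcome has its own defined bounds. This should be fixed before analysis.

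**What to change.** In 'Missing data for the secondary outcome':

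- **Satisfaction:** state that the main analysis is as observed and delete simple mean imputation. As sensitivity analyses, assign missing scores 5 in one arm and 1 in the other, then reverse. These are bounds and do not imply that participants who died were dissatisfied. Multiple imputation may be added; to address MNAR it needs an explicit shift for non-responders.
- **KCCQ:** keep 0 for deaths in both arms. Assign living non-responders 100 in one arm and 0 in the other, then reverse. Keep the all-zero analysis under its own name, worst-worst.

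The cost is a few sentences in the SAP and a little more analysis. Satisfaction intervals will be wider than mean imputation would give. No additional data are needed.

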### Statistical methods to compare primary and secondary outcomes between groups

#### Main analysis of primary outcome

The primary outcome of the trial, “days alive without hospitalisation during the 90 days following randomisation”, is a countable outcome with an anticipated non-normal distribution.

Accordingly, we plan a non-parametric analysis of the primary outcome [16]. We will assess the Mann-Whitney parameter using the Wilcoxon-Mann-Whitney-test on the full analysis dataset according to the intention-to-treat principle [17].

For explorative purposes, the analysis will also be performed on the per-protocol dataset and as-treated dataset.

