### Baseline characteristics

Baseline patient characteristics and demographics will be reported for each group (Table 1 in the final publication).

Table 1: Baseline characteristics

Variable	Data type
Demographics	
Age (years)	Continuous
Sex (female) %(n)	Categorical
Race (white)	Categorical
Included at specialised referral centre %(n)	Categorical
Symptoms and physical examination	
Height (cm)	Continuous
Weight (kg)	Continuous
BMI (kg/m  )	Continuous
Rales %(n)	Categorical
Peripheral oedema %(n)	Categorical
Orthopnoea %(n)	Categorical
Ascites %(n)	Categorical

NYHA class %(n)	Categorical, ordinal
II	
III	
IV	
Fatigue %(n)	Categorical
The CSHA clinical frailty scale score [9,10]	Categorical, ordinal
Score<4 = frail %(n)	
Score>4 = not frail %(n)	
Heart failure characteristics	
LVEF (%)	Continuous
Time since HF diagnosis (months)	Continuous
New-onset HF %(n)	Categorical
Ischemic aetiology %(n)	Categorical
Medical history	
Cardiovascular comorbidities %(n)	Categorical
Atrial fibrillation	
Hypertension	
Comorbidities %(n)	Categorical
COPD	
Diabetes	
CKD	
Liver disease	
Smoking (former or active) %(n)	Categorical
Alcohol over 7 /14 units pr. week (woman/men) %(n)	Categorical
Laboratory values	
Haemoglobin mmol/L	Continuous
Sodium mmol/L	Continuous
Potassium mmol/L	Continuous
Creatinine micromole/L	Continuous
eGFR (mL/min/1.73m  )	Continuous
NT-proBNP (pmol/L)	Continuous
Albumin g/L	Continuous

Troponin T/I above the upper reference limit %(n)	Categorical
C reactive protein mg/L	Continuous
Treatment	
ACEi/ARB/ARNI %(n)	Categorical
Beta-blockers %(n)	Categorical
MRA %(n)	Categorical
SGLT2i %(n)	Categorical
Home loop diuretics %(n)	Categorical
Home loop diuretics dose (furosemide-equivalent dose, mg daily)	Continuous
Anticoagulant therapy %(n)	Categorical
VKA	
DOAC	
LMWH	
ICD %(n)	Categorical
CRT %(n)	Categorical

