#### Analyses of Secondary Outcomes

The number of days alive and not hospitalised due to heart failure has the same assumptions as the primary endpoint and will be analysed as such. Distribution of the secondary outcome continues variables will be determined by visual inspection of the histogram and by QQ plots. Normally distributed continuous variables will be compared by students' t-test and non-normal distributed continuous variables by the non-parametric Wilcoxon-Mann-Whitney-test. Categorical data will be compared using Chi-squared or exact Fisher test if  $n < 5$  in a group. Time-to-event data will be compared by the log-rank method, and adjusted analyses will be performed by proportional hazards regression. The main analysis of KCCQ scores will be a comparison of the mean score at each time point. For further exploratory analyses, the total KCCQ-score at each time point will be summarized in 25-point ranges, where scores represent health status as follows: 0 to 24: very poor to poor; 25 to 49: poor to fair; 50 to 74: fair to good; and 75 to 100: good to excellent [19].

The number and percentage of complications to thoracentesis will be reported. The number and percentage of thromboembolic events within 30 days and complications during the index admission will be compared between the groups. Results will be presented in tables, and time-to-event outcomes will be illustrated by Kaplan-Meier curves.

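### The primary comparison uses no prognostic baseline value; if those listed explain 10–20% of outcome variance, adjustment would be worth roughly 9–32 participants

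*SAP*

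**What the plan says.** Under Main analysis of primary outcome the SAP commits to one comparison: "We will assess the Mann-Whitney parameter using the Wilcoxon-Mann-Whitney-test on the full analysis dataset according to the intention-to-treat principle". No covariate or stratum is named.

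Under Sensitivity analyses it adds three van Elteren tests: one without strata, one by site and one by anticoagulation status. According to the Randomisation section, the last two are the stratification factors.

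Table 1 (Baseline characteristics) lists age, LVEF, eGFR and the row beginning "NT-proBNP (pmol/L" as continuous variables. Age, LVEF and eGFR below 30 return under Subgroup analyses, where they define groups in which the effect is examined. That is not adjustment.

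Adjustment is mentioned once, under Analyses of Secondary Outcomes. For time-to-event data, "adjusted analyses will be performed by proportional hazards regression", with no covariates listed.

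**The concern.** The outcome combines length of the index stay, readmission and death. Patients differ in prognosis on all three, and with about 63 per arm a chance imbalance in prognosis between the arms adds noise to the comparison. Adjusting for baseline values that predict the outcome removes part of that noise without an extra participant, visit or measurement. The SAP accepts adjustment for secondary time-to-event outcomes but plans none for the outcome on which the trial's conclusion rests. No planned analysis of the primary outcome would show whether an imbalance in age, NT-proBNP, renal function or LVEF had influenced the result. What is at stake is precision and power, not validity.

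**Working it through.** **Inputs from the SAP.** Sample Size: "found a total of 126 participants required to detect a difference of three days in the primary endpoint", with alpha "of 0.05 and a power of 90" per cent; 85 days in the intervention arm, "while participants assigned to pharmacological therapy alone will have 82 days, with a shared standard deviation of 5 days"; in-hospital mortality of 5% in both arms. Study design: 1:1 allocation. Statistical principles: "A two-sided p-value" is the criterion. Primary outcome definition: range 0 to 90, with death during the index admission scored 0.

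**Assumed.** R2, the share of outcome (rank) variance explained by the baseline covariates. The SAP gives none, so a range is shown.

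**1. The plan's own figure.** The standardised difference is 3/5 = 0.6. A two-sided t-test at 0.05 with 90% power needs 59.35 per arm, so 60 per arm or 120 in total. Dividing by 0.95 gives 59.35/0.95 = 62.5, so 63 per arm or 126. Dividing by the Wilcoxon relative efficiency of 0.955 also gives 126. The SAP does not say which inflation it used, but 126 is reproducible.

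**2. Precision by formula.** Adjustment multiplies the variance by (1 − R2). The equivalent sample size is 126/(1 − R2), and the gain is that figure minus 126. The last column multiplies the equivalent size by (1 − 4/123), a rough allowance for estimating four coefficients, before subtracting 126.

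| R2 | Equivalent N | Extra participants | Extra after allowance |
|---|---|---|---|
| 0.00 | 126.0 | 0 | −4.1 |
| 0.02 | 128.6 | 2.6 | −1.6 |
| 0.05 | 132.6 | 6.6 | 2.3 |
| 0.10 | 140.0 | 14.0 | 9.4 |
| 0.15 | 148.2 | 22.2 | 17.4 |
| 0.20 | 157.5 | 31.5 | 26.4 |
| 0.30 | 180.0 | 54.0 | 48.1 |

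**3. Power by formula, from the planned 90%.** Power = Φ((1.960 + 1.282)/√(1 − R2) − 1.960).
- R2 = 0.10: 3.242/0.949 − 1.960 = 1.46, giving 92.7%.
- R2 = 0.20: 3.242/0.894 − 1.960 = 1.66, giving 95.2%.

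**4. Simulation on ranks.** Steps 2 and 3 apply a result for means to a rank test, so the gain was also simulated. There were 63 per arm, normal outcomes with means 85 and 82 and SD 5, rounded and capped at 90, and 5% of each arm set to 0. One covariate was unrelated to the zeros. Rank ANCOVA stood in for an adjusted rank analysis, with 3,000 trials per row. R2 here refers to the latent outcome before capping and zeros.

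| Latent R2 | Unadjusted power | Adjusted power | Extra participants |
|---|---|---|---|
| 0.00 | 82.2% | 81.9% | −1 |
| 0.04 | 83.3% | 83.5% | 3 |
| 0.10 | 82.9% | 84.8% | 9 |
| 0.20 | 83.5% | 87.2% | 22 |

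The last column is 126 × (mean variance ratio − 1). For example, 126 × 0.0728 = 9.2 and 126 × 0.1719 = 21.7.

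When the covariate also predicts in-hospital death, adjusted power was 86% at R2 = 0.10 and 90% at R2 = 0.20, against 83% unadjusted. A further run on the SAP's inputs gave 86% and 87–91%, against 82–84% unadjusted, with a type I error of 5.2%.

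Unadjusted power in these runs is below 90% because of the 5% scored 0. Without them the Wilcoxon-Mann-Whitney test had 90.3% power.

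**The case against.** The strongest reply is that nothing here is wrong. An unadjusted Wilcoxon-Mann-Whitney test is valid in a randomised trial. The SAP names its parameter and cites a method for intervals compatible with the test. On this view, covariate adjustment is a preference. The first part stands: a reader might infer that the primary analysis is biased or contradicts the rest of the SAP, and the document supports neither. The last part does not, because a specific gain is available at almost no cost from variables already listed.

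Second, the gain is assumed, not known. A reader might infer that 14 to 32 participants are definitely being given away. Those figures are 126/(1 − R2) − 126 at R2 of 0.10 and 0.20, and the SAP supports no particular R2. Simulation with a covariate unrelated to in-hospital death gave 9 and 22. Eligibility limits LVEF to 45% or below and excludes eGFR below 15, which may weaken both as predictors. This objection stands and is why the size is stated conditionally.

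Third, Table 1 gives data types, not completeness, so one cannot infer that all four values exist for every participant. A rule for missing baseline values is needed.

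Fourth, rank ANCOVA does not itself estimate the Mann-Whitney parameter. That stands too. Rank ANCOVA serves above only to gauge the gain; the remedy should be a method that keeps the parameter.

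Fifth, baseline factors are not wholly ignored, since anticoagulation status is a patient characteristic. But it enters as a randomisation factor in a sensitivity test, and no analysis of the primary outcome uses the four values at issue.

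**Conclusion.** The point holds as a missed gain in precision. Neither the primary comparison nor its sensitivity tests use a prognostic baseline measurement, although four plausible ones are listed.

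If these covariates explain 10–20% of the outcome (rank) variance, adjustment is worth roughly 9 to 32 participants: 9 and 22 in the simulation, 14 and 32 by formula. Over R2 of 0.02 to 0.30 the formula gives about 3 to 54. From the planned 90%, power would become about 93–95% by formula. Under the SAP's inputs with 5% scored 0, simulated power rises from about 82–84% to about 85–91%. If the covariates prove weak, there is little or no gain, and possibly a loss equivalent to a few participants.

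The unadjusted power near 83% in those runs might be read as part of this point. It comes from the zeros and is a separate sample-size question.

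**What to change.** Under Main analysis of primary outcome, prespecify a Mann-Whitney estimate with randomisation-based covariance adjustment for age, log NT-proBNP, eGFR and LVEF. Set missing baseline values to the overall median across both arms. This keeps the parameter the SAP already names. Report the unadjusted Wilcoxon-Mann-Whitney test beside it, and state which of the two carries the conclusion.

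If the sponsor prefers to leave the main analysis as it is, make the adjusted estimate the first item under Sensitivity analyses.

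In either case the covariates, their scale and the missing-value rule must be fixed before outcome data are examined. This matters especially in an open-label trial, where a later choice would not be credible.

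The cost is a few lines of SAP text and R code, and one more step to explain. No new data are needed. If the adjusted estimate becomes the main analysis, the protocol's description of that analysis must agree; this could not be checked from the SAP alone.
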